2.1 Description of the PLWHIV Questionnaire and Schedule for Completion

The PLWHIV questionnaire consists of two validated instruments and tailored items written for this study. The validated instruments are the FIM and AIM, described below. The tailored items ask PLWHIV about a number of topics, including preferences and attitudes regarding their medication regimen.

PLWHIV will be asked to complete a questionnaire at Baseline/ Month 1 and at Months 3 and 8 (see table above).

Table B. Questionnaire Administration for PLWHIV

Questionnaire	Baseline/ Month 1	Month 3	Month 8
Feasibility of Intervention Measure	Х	Х	Х
Acceptability of Intervention Measure	Х	Х	х
PLWHIV Tailored Items	х	Х	х

Abbreviation: PLWHIV = participants living with human immunodeficiency virus

2.1.1 Feasibility of Intervention Measure

The FIM (four items) is employed to evaluate the feasibility of an implementation strategy and assess perceived intervention feasibility. Items are measured on a five-point rating scale (1=201), 3=201, 3=201, 4=201, 5=201, 5=201). The FIM was validated with other implementation outcome measures. Higher scores indicate greater feasibility. There are no reverse-scored items on the FIM, and the mean score for feasibility of the intervention is calculated by averaging the responses from the four items.

2.1.2 Acceptability of Intervention Measure

The AIM (four items) is employed to evaluate the acceptability of an implementation strategy and assesses perceived intervention acceptability. The items are measured on a five-point rating scale (1= $\frac{\text{CCI}}{\text{CCI}}$, 2= $\frac{\text{CCI}}{\text{CCI}}$, 3= $\frac{\text{CCI}}{\text{CCI}}$, 4= $\frac{\text{CCI}}{\text{CCI}}$, 5= $\frac{\text{CCI}}{\text{CCI}}$). The AIM was validated with a suite of implementation outcome measures. Higher scores indicate greater acceptability. There are no reverse-scored items on the AIM, and the mean score for acceptability of the intervention is calculated by averaging the responses from the four items.

2.1.3 PLWHIV Additional Questionnaire

The tailored PLWHIV questionnaire was developed specifically for this study and contains items regarding the reasons for switching to CABENUVA, adherence to their previous oral HIV medication, preferences and attitudes regarding their medication regimen, and perceived advantages and disadvantages of receiving injections at the IC/ASA. The Baseline/ Month 1 PLWHIV questionnaire has 34 items (including the FIM and AIM), and the Month 3 and Month 8 questionnaires have 39 items, will be a hybrid of paper and CRF (Medidata).

2.1.4 Data Management

The Baseline/ Month 1 PLWHIV questionnaires will be collected by electronic data capture (EDC) via MediData rave using tablets at the study sites. Subsequent questionnaires will also be collected by EDC. Any questionnaires completed on paper, due to issues with EDC devices for example, will be entered into the EDC at the sites by clinical staff. Queries will focus on issues of missing data. Missing surveys will be queried (by e-mail) to the IC/ASA staff member, to verify that surveys were completed. If data are still missing, follow-up queries will be initiated by the study team with respective IC/ASA staff. Queries remaining open from unresponsive IC/ASA staff may be closed with GSK/ViiV review and approval.

2.2 Windows for Questionnaire Completion

Baseline/Month 1 is defined as the date when a participant signs the Informed Consent Form (ICF) and completes Baseline/Month 1 protocol procedures prior to receiving the first study related CABENUVA injections at the IC/ASA

All additional study visits, including those where questionnaires and/or interviews are administered at Months 3 and 8 will be anchored off of each participant's Month 1 visit, so it will reflect the months on study, regardless of what dosing regimen the participant is on (e.g., monthly or every 2 months) and regardless of whether they have missed any injections and received oral bridging.

At Month 1, questionnaires should be completed after signing the ICF and before receiving CABENUVA intramuscular (IM) injections or within 14 days following the Month 1 visit. Questionnaires should be completed before receiving CABENUVA IM injections or +/- 14 days following the last visit.

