#### Type of Participant and Disease Characteristics

- 2 HIV-1 infected and have been prescribed CABNEUVA per the USPI. Participants can be enrolled:
  - If they have been taking oral VOCABRIA + EDURANT or other ART for approximately 1 month (at least 28 days) prior to Baseline/Month 1, or
  - Already taking CABENUVA prior to Baseline/Month 1 and the last injections
    were within a 1 month ± 7-day window or for every 2-month injections, the
    timing will vary they are receiving the initiation injections (1 month ± 7-day) or
    the continuation injections (2 months ± 7 days) per the USPI, or
  - Prescribed direct to inject and receive their 1st injection without an oral lead in at the Infusion Center on the last day of any other antiretroviral therapy.

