#### **ANNEX 1: SCHEDULE OF ACTIVITIES**

Procedure 	Baseline/			Treatme	ent Period (	Months)			E.D. 	Notes
riocedure	Month 1 	2	3	4	5	6	7	8	L.D.	Notes

- 1. The timing and number of planned study assessments may be altered during the study based on newly available data.
- 2. The following sequence of events must be followed for participants at the Baseline/Month 1 visit: 1) Informed consent form (ICF) Consent 2) Confirm Inclusion and Exclusion criteria 3) complete questionnaires and assessments, 4) Receive first study related intramuscular (IM) injections at the IC/ASA. Baseline is defined as the Month 1 visit.
- 3. E.D = early discontinuation/ withdrawal: This visit should only be conducted if the participant discontinues from the study, and the discontinuation/withdrawal reason should be recorded.

NOTE: Carefully follow the Instructions for Use when preparing and administering CABENUVA IM to avoid accidental intravenous administration

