#### **Participants**

Baseline/Month 1 is defined as the date when a participant signs ICF and completes Baseline/Month 1 protocol procedures prior to receiving the first study related CABENUVA injections at the IC/ASA

All additional study visits, including those where questionnaires and/or interviews are administered at Months 3 and 8 will be anchored off of each participants Month 1 visit, so it will reflect the Months on study, regardless of what dosing regimen the participant is on (e.g., monthly or every 2 monthly) and regardless of whether they have missed any injections and received oral bridging.

Procedure 	Baseline/			Treatme	ent Period (	Months)			- E.D. 	Notes
Flocedule.	Month 1 	2	3	4	5	6	7	8	E.D.	Notes
Participant	X		Х					X	Х	At Month 1, Questionnaires should be completed after signing the ICF and before receiving CABENUVA IM injections or within 14 days following the Month 1 visit.
Questionnaires									A	Questionnaires should be completed before receiving CABENUVA IM injections or $\pm$ 14 days following the last visit.
Participant Interviews								Х	Х	Interviews will be completed at the participants last study Visit: Month 8 or early withdrawal visit. Interviews can be completed 2 weeks before or 2 weeks following the last visit.
•										Interviews should be completed before receiving CABENUVA IM injections if interviews are completed the day the injections are administered.

**Expert Panel**: will consist of key IC/ASA staff members involved in decision making and/or oversee daily operations at the IC/ASA, selected HIV care providers that may refer PLWHIV, and ViiV Healthcare (VHC). Panel members will meet prior to Baseline/Month 1 to design the Blueprint (Section 5.1.1)

Baseline/Month 1 is defined as the date when a participant signs ICF, completes protocol procedures and receives the first study related CABENUVA injections at any infusion center.

Month 3 and Month 6 assessments are to be completed after approximately 10 participants (across all ICs/ASA) have completed their Month 3 and Month 6 study visits at any IC/ASA site

Expert Panel X	X (Prior to					FIM, AIM (FIM and AIM also completed prior to FPFV at the Baseline/Month 1 visit)
F	Month 1)	X		Х		Meetings will be held as required over the first 6 months to discuss any iterations that are needed to refine and optimize the blueprint.
Questionnaires N	Month 1)	^		^		months to disc

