	Removed all text regarding a 12-month recruitment period	The recruitment period for some sites may be longer than or less than 12 months
Section 4.1 Study Design	Modified schema	In the Participants design removed one set of the questionnaire/interview symbols for clarity  Added footnote to explain how the blueprint will be revised outside of the Expert Panel
Section 4.2 Study Population	Removed all text regarding a 12-month recruitment period	The recruitment period for some sites may be longer than or less than 12 months
Section 4.2.1.2 Exclusion Criteria	Removed Exclusion Criteria 4	To allow participants into the study regardless of how many prior (pre-study) injections of CABENUVA they have received at the IC
Section 4.3.2 HIV Care Providers	Revision to number of IC sites	Increased the approximate number of IC sites to include the additional ICs

Section # and Name	Description of Change	Brief Rationale
Section 4.3.3 Infusion Center Staff	Minor text changes	Clarification of text
Section 5.1.1 Expert Panel	Added text regarding the additional ICs entering the study	New information
Section 5.1.2 Implementation Assessments Section 6 Statistical Considerations	Added baseline analysis	To gain insights on the initial assessment of implementation science data on primary and key secondary objectives
Section 6.1 Study Size	Revision to number of IC sites	Increased the approximate number of IC sites to include the additional ICs
	Removed all text regarding a 12-month recruitment period	The recruitment period for some sites may be longer than or less than 12 months
Annex 1 Schedule of Activities	Corrected several errors in text and in the Month of assessment	Clarifications
Annex 5 Protocol Amendments	Moved Protocol Amendment 3 Table of Changes to Annex 5	

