Abbreviations: AIM = Acceptability of Intervention Measure; ASA=Alternative Site of Administration; FIM = Feasibility of Intervention Measure; IC = infusion center; QAP = Qualitative Analysis Plan

2 Study Design

This is a Phase 4, single-arm, open-label, multi-center study examining the administration of CABENUVA IM in ICs/ASAs in the United States. This study is being conducted following Food and Drug Administration (FDA) approval and commercial availability of CABENUVA. Eligible and consenting PLWHIV will be followed for eight months to evaluate an implementation blueprint for IM administration of CABENUVA for HIV-1 treatment at ICs/ASAs. The total duration for study PLWHIV is approximately eight months from the time of enrollment and receipt of the first administration of CABENUVA IM injections at the IC/ASA.

Relevant to this SAP, up to 120 PLWHIV who have been prescribed CABENUVA by their HIV care provider will be asked to complete questionnaires per the Schedule of Activities (SoA; see ANNEX 1 in protocol), as follows:

- Baseline/Month 1 questionnaires should be completed prior to receiving the first CABENUVA injections
- Baseline/Month 1 for each PLWHIV is defined as the date when a PLWHIV signs the informed consent form and completes Baseline/Month 1 protocol procedures prior to receiving the first CABENUVA injections at the IC/ASA
- Months 3 and 8 will be anchored off of each PLWHIV Baseline/Month 1 visit, so it will reflect the Months on study, regardless of what dose they are on and regardless of whether they have missed any injections and received oral bridging.

PLWHIV questionnaires consist of the Feasibility of Intervention Measure (FIM) and the Acceptability of Intervention Measure (AIM), as well as a tailored questionnaire.

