3.1 Missing Data Handling Scheme

Missing data at the multi-item scale level for standardized scales (FIM and AIM) will be addressed with standard proration rules²: if at least 50% of the items are completed the scale will be scored by taking the mean of the completed items, unless otherwise specified for a particular outcome. Following this, partially completed FIM and AIM administrations will be scored if two, three, or four items are completed, and will not be scored if only one item is completed. Items not completed will be logged as

missing data. No missing data will be imputed. Table shells for missing data from FIM and AIM scales can be found in Appendix A.

3.2 Cross-sectional Univariate Distributions of Study Variables and Features of Score Distributions

For questions with ordinal responses, a univariate distribution of every item will be tabulated. Standard distributional statistics will be tabulated for interval-like (ordinal) variables, including mean, SD, median, percentage missing, range (minimum and maximum of responses), percentage of the sample at the ceiling (highest possible score) and floor (lowest possible score), first and third quartiles, and 95% CIs. For questions with descriptive responses, a frequency distribution of all responses will be presented with n (%).

3.3 Distributions of Study Variables and Features of Score Distributions, Change from Baseline/ Month 1 for FIM and AIM

The univariate distribution of item change scores (Month 3 minus Baseline/ Month 1, Month 8 minus Baseline/ Month 1, and Month 8 minus Month 3) will be tabulated for the FIM and AIM, both in terms of distributional characteristics of change and frequency of responses. Distributional characteristic tables will include the SD of the change distribution, median change, first and third quartiles, and 95% CIs. Change analyses will be limited to those PLWHIV completing questionnaires at Baseline/ Month 1 and each respective timepoint. Categorical data for the FIM and AIM will be presented in shift analyses showing the frequency of change by the degree of shift across response categories and will be presented for Baseline/ Month 1 to Month 3, Baseline/ Month 1 to Month 8, and Month 3 to Month 8.

4 Fidelity to Treatment in Dosing Window

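### The participant SAP lets a Month 1 FIM/AIM form completed up to 14 days after the first study injection serve as baseline, against its own pre-injection definition, which blurs the secondary change endpoints

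*SAP*

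**What the plan says.** Four places in the current documents time the participant's Month 1 form, and they do not agree.

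- Participant SAP, Section 2 (Study Design): "Baseline/Month 1 questionnaires should be completed prior to receiving the first CABENUVA injections". No later allowance is given.
- Participant SAP 2.2, opening definition: baseline is the date on which the participant signs consent and "completes Baseline/Month 1 protocol procedures prior to receiving the first study related CABENUVA injections at the IC/ASA". Protocol 5.1.3 defines it the same way.
- Protocol Annex 1, note 2, a sequence the site is obliged to keep: steps 3 and 4 are "complete questionnaires and assessments, 4) Receive first study related intramuscular (IM) injections at the IC/ASA".
- Participant SAP 2.2, window rule: "before receiving CABENUVA intramuscular (IM) injections or within 14 days following the Month 1 visit". The participant questionnaire row of Annex 1 has the same allowance: "before receiving CABENUVA IM injections or within 14 days following the Month 1 visit".

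On analysis, participant SAP 3.3 computes Month 3 and Month 8 differences from baseline for FIM and AIM and states: "Change analyses will be limited to those PLWHIV completing questionnaires at Baseline/ Month 1 and each respective timepoint". SAP 2.3 keeps out-of-window forms in the main analysis and removes them in a sensitivity analysis, pointing to Section 2 for the window.

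On entry, inclusion criterion 2 admits people "Already taking CABENUVA prior to Baseline/Month 1 and the last injections" fell in a set interval. The current exclusion list has no cap on earlier injections. The stated reason for dropping the former cap was "To allow participants into the study regardless of how many prior (pre-study) injections of CABENUVA they have received at the IC".

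**The concern.** The SAP describes the intervention as the process of using the center as the place to receive injections. A form completed after the Month 1 injection is therefore a rating made after the first study exposure to that process. If it is labelled baseline, the Month 3 and Month 8 differences no longer run from before to after that exposure for those participants, and the tables mix the two kinds of difference without marking them.

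Change in FIM and in AIM at Months 3 and 8 are stated secondary endpoints. Tables 2.1, 2.2, 5.1, 5.2, 6.1 and 6.2 all draw on this baseline. The conflict also reaches the deviation counts: a form at day 7 is on time under SAP 2.2 and late under Section 2, so two programmers could fill the late row of Table 7, and build the sensitivity set, differently.

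**Working it through.** The plan gives no figure to reproduce here. The check compares texts, then does date and visit arithmetic, then a labelled illustration.

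**1. Is a day +1 to +14 form out of window?** SAP 2.3 defers to Section 2. The Section 2 bullet says yes. The window rule in 2.2 says no. The heading of 2.2 makes it the more natural reference, in which case the sensitivity analysis keeps the form. The text allows either reading. Forms later than day 14 stay in the main analysis in any case.

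**2. What does the form itself assume?** In Table 1.3.1 the baseline item on visit length asks what the participant expects. In Table 1.3.2 the Month 3 item asks about actual time, leaving out the first visit. The baseline version is written for someone who has not yet had the visit.

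**3. How much of the interval can be lost?** By calendar, Month 1 to Month 3 is 59 to 62 days and Month 1 to Month 8 is 212 to 215 days.
- Share used by a +14-day form, to Month 3: 14/62 = 22.6% to 14/59 = 23.7%.
- Share to Month 8: 14/215 = 6.5% to 14/212 = 6.6%.
- If a 14-day margin on either side also applies at Month 3, the shortest gap between two in-window forms is 59 − 28 = 31 to 62 − 28 = 34 days.

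**4. Study injections received before each form (Annex 1 dosing rows, Month 3 form done before that day's injection).**

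| Schedule | Baseline, pre-injection | Baseline, post-injection | Month 3 |
|---|---|---|---|
| Monthly | 0 | 1 | 2 |
| Every 2 months, initiating (Months 1, 2, 4, ...) | 0 | 1 | 2 |
| Every 2 months, continuing (Months 1, 3, 5, 7) | 0 | 1 | 1 |

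For a continuing every-2-month participant with a late baseline form, the count is 1 at both time points. That difference contains no added study exposure.

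**5. Illustration of the bias.** Let D be the true change, f the share of baseline forms completed after the first study injection, and s the share of D already present on those forms. Assume late completers are otherwise like the rest. The observed baseline is then B + f·s·D, and the observed change is D(1 − f·s). With D = 10 points:
- f = 0.10, s = 0.25: 10 × (1 − 0.025) = 9.75
- f = 0.25, s = 0.50: 10 × (1 − 0.125) = 8.75
- f = 0.50, s = 0.50: 10 × (1 − 0.25) = 7.5
- f = 0.50, s = 1.00: 10 × (1 − 0.50) = 5.0

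If the first visit moves opinion the opposite way to the eventual change, s is negative and the change is exaggerated: f = 0.25, s = −0.50 gives 10 × (1 + 0.125) = 11.25. The documents give neither f nor s.

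**The case against.** Several points on the other side stand.

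- The endpoint is worded as change over time from a Month 1 anchor, not as change from a state of no exposure. The study is single-arm and these tables are descriptive.
- Late forms may be few. The pre-injection order is mandatory, and SAP 2.1.4 has forms collected on tablets at the site.
- Deleting the 14 days would not create an unexposed baseline. The form is taken at the center, after insurance checks for people new to the drug, and one baseline item asks in the past tense how acceptable those checks were.
- A reader might infer that the plan ignores people already receiving injections. It does not. The protocol Abstract and Section 6.2 commit to subgroups that include initiation method and number of injections before enrollment. Participant SAP Section 3 repeats them, though only as factors that may be used, with details to be added.
- A reader might also want to split by whether earlier injections were given at a center. The baseline items shown record whether and how many, not where. A split of no prior injection at a center versus any prior injection would also put someone injected only at the provider's office in both groups.

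None of this removes the contradiction in the timing text, or the fact that a post-injection form can enter the change rows as baseline.

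**Conclusion.** The conflict is real and sits in current text. As written, a form completed after the first study injection can serve as baseline in six change and shift tables, and the sensitivity analysis meant to handle timing is ambiguous about it. The bias affects only the secondary change endpoints that start from Month 1 and how the Month 1 proportions are interpreted. The Month 8 primary proportion and the Month 3 to Month 8 rows are untouched.

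A reader might infer that the reported change is heavily diluted, for instance a 25-point gain shrinking to 10. The documents do not support that. It needs an invented share of late forms (60%) and the assumption that one visit produces the entire shift (25 × (1 − 0.6 × 1) = 10). Size and direction both remain unknown, and the figures in the illustration only show sensitivity to f and s. Nor do the documents establish that earlier injections at the center make the baseline invalid. They show that a listed subgroup has not been finalised in version 4.0 of the SAP.

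**What to change.** 1. Reconcile participant SAP Section 2, SAP 2.2, Annex 1 note 2 and the Annex 1 questionnaire row, so that the baseline used for change is a form completed before the first on-study injection.
2. Derive a flag for forms dated after that injection. For forms completed on the injection day, use the completion time where it is recorded, and state the rule for those without one.
3. Exclude flagged forms from the baseline-to-Month 3 and baseline-to-Month 8 parts of Tables 2.1, 2.2, 5.1, 5.2, 6.1 and 6.2. At minimum, rerun those parts without them and say in SAP 2.3 that such forms count as out of window for this purpose. Keep them in the cross-sectional Month 1 rows, and report how many there are.
4. In participant SAP Section 3, commit to presenting the change rows for participants with no CABENUVA injection before enrollment and for those with one or more, without using the place of earlier injections. Take this from the pre-enrollment exposure data that the clinical SAP already tabulates (Table 14.1.9). The questionnaire item asks about injections before the day of completion, so a late form could count the study injection as a prior one.

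Cost: SAP wording, one derived flag from dates the study should already hold, and fewer pairs in the change rows of a study capped at 120. Changing the Annex 1 row is a protocol change. If collection is already finished, steps 2 to 4 can be done in the SAP alone.

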2.3 Conditions for Inclusion in Analytic Dataset

Duplicate Questionnaires

In the instance that duplicate questionnaires are present for the same participant at the same visit, the temporally first-administered questionnaire will be included in the analytical dataset if it is fully completed. If the first questionnaire is not fully completed and the temporally second-administered questionnaire is fully completed, then the second questionnaire will be included in the analytical dataset. If neither questionnaire is fully completed, the temporally first-administered questionnaire will be included in the analytical dataset.

Out-of-Window Questionnaires

Questionnaires will not be excluded for being out of temporal window (see Section 2). A sensitivity analysis will be performed for all analyses described in the current SAP that pertain to FIM or AIM items, with all out-of-window questionnaires removed. Results of these analyses will be compared to the main analyses, and the magnitude of differences will be summarized descriptively.

